5.4.3. Other Secondary Endpoint: CGI-I at Day 42, in DGM4-Positive Patients

CGI-I at Day 42 (Visit 7) will be analyzed using the CMH test stratified by region. Summary statistics will be provided on the proportion of subjects in each category. Summary statistics on CGI-I as a continuous variable will also be provided including the mean and median.

5.4.4. Other Secondary Endpoint: Change in SDS from Baseline to Day 42, in DGM4-Positive Patients

The change in SDS from baseline (Visit 3, Day -1) to Day 42 (Visit 7) will be analyzed using the MMRM model without imputation similar to the one used in sensitivity analysis (2) for the primary efficacy endpoint described in Section 5.4.1.3.

5.4.5. Subgroup Analyses

Subgroup analyses for the primary endpoint will be considered for gender, ethnicity, and region, and may be explored for other factors (such as duration of MDD baseline severity in term of MADRS total score). Summary statistics will be provided for efficacy measures by treatment for each subgroup.

5.5. Safety Analysis

5.5.1. Adverse Events

Adverse events will be coded using MedDRA Version 25.0 or higher.

A TEAE is any AE that starts on or after the first day of study treatment or that worsens on or after the first day of study treatment, and within 30 days of the last administration of study treatment.

For the purpose of regulatory reporting, relationships of "Related" or "Unrelated" will be assessed and presented. Related to study drug suggests there is as at least a reasonable possibility that the drug caused the AE (ie, there is evidence or arguments to suggest a causal relationship between the drug and AE).

Unrelated to study drug will be assessed based on the following:

- Does not follow a reasonable temporal sequence from administration of drug
- Does not appear to worsen when the drug is re-administered
- There is not a reasonable possibility that the drug caused the AE
- An alternate etiology has been established, ie, the AE is more likely explained by another cause (eg, other study treatments or procedures, underlying medical conditions, concomitant medications, etc) than the study treatment

Missing relationships will not be imputed.

Potential liver injury, ie, suspected and/or confirmed Hy's Law, and drug-induced liver injury (DILI) cases will be assessed as adverse events of special interest (AESIs) and must be reported as serious adverse events. Information of abnormal laboratory test results including the course and evolvement, clinical signs and symptoms, detailed medical history and concurrent medication, history and current lifestyle including alcoholic assumption, and history of exposure to environmental chemical agents will be used to assess the case(s).

An overall summary of TEAEs using frequencies and percentages of subjects will be presented based on the following categories:

- TEAEs
- Study drug related TEAE
- TEAE by worst severity
- Serious TEAE
- Study drug related serious TEAE
- TEAEs leading to study drug withdrawal
- TEAEs leading to study drug being on hold
- TEAEs leading to death
- AESIs

The following events will be tabulated by SOC and PT. SOC will be sorted by descending frequency and then alphabetically for tie. Within each SOC, PT will also be sorted by descending frequency and then alphabetically for ties, by the overall number of subjects. If a SOC or PT is reported more than once for a subject, the subject will only be counted once in the incidence for that SOC or PT.

- TEAEs
- Study drug related TEAE
- TEAE by worst severity
- Serious TEAE
- Study drug related serious TEAE
- TEAEs leading to study drug withdrawal
- TEAEs leading to study drug being on hold
- TEAEs leading to death
- AESIs

Summaries of events by decreasing frequency of PT include:

- TEAEs
- Study drug related TEAE
- Serious TEAE
- Study drug related serious TEAE

If a PT is reported more than once for a subject, the subject will only be counted once in the incidence for that PT.

The following listings will be provided:

- All AEs (flag TEAE)
- Serious Aes (flag TEAE)
- TEAEs leading to study drug withdrawal
- TEAEs leading to study drug being on hold
- TEAEs leading to death
- AESIs

5.5.2. Clinical Laboratory Evaluation

Blood chemistry, hematology, and urinalysis tests are listed in Table 3.

Table 3. Clinical Laboratory Tests

Blood Chemistry	Hematology	Urinalysis
 Alanine aminotransferase (ALT/SGPT) Alkaline phosphatase (ALP) Aspartate aminotransferase (AST/SGOT) Bilirubin (direct and total) Blood urea nitrogen (BUN) Calcium Chloride Cholesterol (total) Creatine kinase (CK) Creatinine Glucose (serum) Phosphorus Potassium Protein (albumin and total) Sodium 	 Hematocrit Hemoglobin MCH concentration (MCHC) Mean corpuscular hemoglobin (MCH) Mean corpuscular volume (MCV) Platelet count Red blood cell (RBC) count White blood cell (WBC) differential Neutrophil count (absolute and %) Lymphocyte count (absolute and %) Monocyte count (absolute and %) Eosinophil count (absolute and %) Basophil count (absolute and %) WBC count 	 On-site macroscopic examination Central lab microscopic examination (in the event of protein, blood, nitrite and/or leukocyte esterase noted in macroscopic) Bilirubin Blood (occult and cells) Ketones Leukocytes Nitrite pH Protein Specific gravity Urobilinogen

Actual value, change from baseline, and percentage change from baseline for continuous parameters (analytes) of blood chemistry and hematology tests will be summarized by visit and treatment group using descriptive statistics (mean, median, SD, minimum, maximum, and number of subjects).

Baseline and post-baseline blood chemistry and hematology tests will be classified according to normal ranges as low, normal, and high. Shift of these tests from baseline to the maximum post-baseline values will be presented by treatment group using the number and percentage of subjects at each shift category. If applicable, some laboratory tests have two directions: hypo and hyper, where both directions will be presented in the shift table.

Liver function tests will be summarized by the following:

- Alkaline Phosphatase (ALP)
 - \circ >1.5 × ULN
 - $\circ >2 \times ULN$
 - \circ >3 × ULN
- Alanine Aminotransferase (ALT)
 - $\circ \quad > 3 \times ULN$
 - \circ >5 × ULN
 - \circ >10 × ULN

- Aspartate Aminotransferase (AST)
 - \circ >3 × ULN
 - \circ >5 × ULN
 - $\circ \quad > 10 \times ULN$
- Total Bilirubin (TBL)
 - \circ >1.5 × ULN
 - \circ >2 × ULN
 - \circ >3 × ULN

ULN = upper limit of normal

The risk difference between treatment arms vs placebo, and 95% confidence interval will be calculated.

All laboratory values will be presented in data listings.

All other laboratory tests, including urinalysis, thyroid, pregnancy, and urine drug screen, will be presented in a data listing only.

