#### 1.2.2.2. Preclinical Toxicity

Liafensine has a moderate potential for acute toxicity. Single oral doses up to 20 mg/kg were tolerated in the rat, and a dose of 0.6 mg/kg was tolerated in monkeys, with clinical findings consistent with targeted inhibition of monoamine reuptake including stereotypic behaviors and elevations in body temperature; increased activity, abnormal respiration in rats; and decreased feeding behavior and evidence of skeletal muscle injury in monkeys.

After repeated dosing, liafensine was clinically tolerated up to 3 mg/kg/day in rats and 1 mg/kg/day in monkeys for up to 3 months. The primary treatment-related findings were pharmacologically-mediated effects including decreases in food consumption and body weight,

increased activity, and stereotypic behaviors at all doses. Target organs were limited to skeletal muscle in rats and monkeys after 2 weeks of dosing and the liver in rats after chronic dosing.

Liafensine-related skeletal muscle injury and repair, which may have been a consequence of pharmacologically mediated increases in activity and/or direct adrenergic stimulation, were observed only at higher doses in rats (up to 6 mg/kg/day) and monkeys (up to 5 mg/kg/day) after dosing (area under the curve [AUC] multiples at ≥ 12-fold in the rat and 3.8-fold in the monkey). The generally minimal severity and limited distribution of these drug-related skeletal muscle changes likely accounted for the absence of correlative increases in serum muscle-related enzymes (AST, CK). There was no skeletal muscle injury noted in rats or monkeys after 3 months of dosing at systemic exposure multiples up to 61- and 4-fold, respectively. The lack of liafensine-related effects on the skeletal muscle after 3 months suggests accommodation with repeat dosing. Routine evaluation of serum AST and CK activities are anticipated to be adequate for monitoring for the development of skeletal muscle changes in humans in the clinical studies.

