## **Table 3:** Laboratory Tests

## **Blood chemistry**

- Alanine aminotransferase (ALT/SGPT)
- Alkaline phosphatase (ALP)
- Aspartate aminotransferase (AST/SGOT)
- Bilirubin (direct and total)
- Blood urea nitrogen (BUN)
- Calcium
- Chloride
- Cholesterol (total)
- Creatine kinase (CK)
- Creatinine
- Glucose (serum)
- Phosphorus
- Potassium
- Protein (albumin and total)
- Sodium

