## 8.3.4. Safety Analyses

The safety analyses will be conducted in the safety population, which includes all randomized patients who have received at least one dose of study drug. The safety population will be analyzed by the actual treatment received regardless of treatment randomized.

Adverse events will be coded using the current version of the Medical Dictionary for Regulatory Activities (MedDRA) classification system. Listings will include the verbatim term, preferred term, and system organ class. The incidence and severity of treatment-emergent adverse events (TEAEs) will be summarized by treatment. Vital signs including supine (after at least 5 min rest) and standing (after 1 min and 3 min standing), blood pressure and heart rate and heart rate, weight, ECG, clinical laboratory evaluation, DESS scale, and C-SSRS data will be summarized with descriptive statistics, by visit and by treatment.

Safety and tolerability data will be summarized descriptively, including tables, listings, and graphs, as appropriate. Unless otherwise stated, descriptive summary statistics for continuous variables will include number (N), mean (ie, arithmetic mean), standard deviation (SD), minimum, median, and maximum. Descriptive summary statistics for categorical data will include frequency and proportion.

All data will be presented by treatment regimen.

Individual data for vital signs including supine (after at least 5 min rest) and standing (after 1 min and 3 min standing), blood pressure and heart rate, weight, clinical laboratory measures, and ECG assessments will be listed and summarized for any potentially clinically important (PCI) values according to predetermined PCI criteria.

There will be no imputation (substitution) for missing data unless explicitly specified otherwise in this protocol or in the statistical analysis plan.

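### CK is one of two named monitors for muscle changes, but the SAP plans no count of patients with marked CK elevation by arm

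*SAP*

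**What the plan says.** Protocol 1.2.2.2 reports skeletal muscle as a target organ in rats and monkeys and concludes: "Routine evaluation of serum AST and CK activities are anticipated to be adequate for monitoring for the development of skeletal muscle changes in humans". CK is in the required chemistry panel (Protocol Table 3), which is run at every visit with laboratory tests.

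SAP 5.5.2 treats laboratory data in four ways:

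- **By-visit summaries.** Every continuous chemistry analyte, CK included, is shown by visit and treatment group as actual value, change and percentage change, with n, mean, median, SD, minimum and maximum.
- **Shift table.** Values fall into three classes ("Baseline and post-baseline blood chemistry and hematology tests will be classified according to normal ranges as low, normal, and high"), and "Shift of these tests from baseline to the maximum post-baseline values will be presented by treatment group".
- **Threshold table.** "Liver function tests will be summarized by the following": ALT and AST above 3, 5 and 10 times ULN, and ALP and total bilirubin above 1.5, 2 and 3 times ULN, with risk differences against placebo and 95% confidence intervals. CK is absent.
- **Listing.** All laboratory values are listed.

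Two general provisions also bear on CK. Protocol 8.3.4 says laboratory measures will be listed and "summarized for any potentially clinically important (PCI) values according to predetermined PCI criteria". SAP 3.5 says laboratory values will be graded mild, moderate or severe. Neither document gives cut-offs for either provision, SAP 5.5.2 has no table for either, and SAP Table 4 (changes from the protocol) does not record the first as dropped.

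**The concern.** The two enzymes named together as muscle monitors are reported unequally. AST has graded patient counts by arm with a comparison against placebo. CK, which is not in the liver panel, has a single undivided high class. A value just above normal and a value many times normal add the same amount to that class.

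At stake is whether the report can say, from a pre-specified table, how many patients per arm had a marked CK rise. Without cut-offs fixed in advance, anyone who wants that number must count from the listing after unblinding, using thresholds chosen with the data in view. The SAP avoids this for liver tests, for blood pressure (5.5.3) and for QTcF (5.5.5).

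**Working it through.** The plan states no figure on this point, so there is none to reproduce. The check has two parts.

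**1. What each planned output can show for CK**

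| Output | Does a marked value show by arm? | Are patients with marked values counted? |
|---|---|---|
| Mean, median | Weakly or not at all | No |
| SD, maximum, by visit | Yes | No |
| Low/normal/high shift | No, one high class | No |
| ULN-multiple table | CK not included | No |
| Clinically important values (Protocol 8.3.4) | No criteria, no SAP table | No |
| Mild/moderate/severe (SAP 3.5) | No cut-offs, no table | No |
| Listing | Yes, by patient | Only by hand, afterwards |

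SAP 3.4 also mentions a summary of worst change from baseline. It is not tied to CK or to any threshold, and SAP 5.5.2 does not define it.

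**2. Illustration**

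Arm size comes from the design: about 180 patients randomised 1:1:1, so 180/3 = 60. The CK values are assumptions: 54 patients at 0.6 × ULN and six above normal, of whom k are at 10 × ULN and 6 − k at 1.5 × ULN.

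Mean = (54 × 0.6 + k × 10 + (6 − k) × 1.5) / 60

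- k = 0: (32.4 + 0 + 9.0)/60 = 0.69
- k = 1: (32.4 + 10 + 7.5)/60 = 0.83
- k = 3: (32.4 + 30 + 4.5)/60 = 1.115

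| k | High class | Median | Mean | SD | Maximum | Above 5 × ULN |
|---|---|---|---|---|---|---|
| 0 | 6/60 | 0.60 | 0.69 | 0.27 | 1.5 | 0 |
| 1 | 6/60 | 0.60 | 0.83 | 1.23 | 10 | 1 |
| 3 | 6/60 | 0.60 | 1.115 | 2.07 | 10 | 3 |

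The shift row is the same in all three cases. The maximum and SD separate k = 0 from the other two. Between k = 1 and k = 3 the maximum is the same. The mean and SD differ, but the number of patients cannot be read from them.

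The maximum leaves the count open whenever two or more patients in an arm have marked values. For a true rate p (assumed), the chance of this among 60 patients is 1 − (1 − p)^60 − 60p(1 − p)^59:

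- p = 1%: 12%
- p = 3%: 54%
- p = 5%: 81%

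**The case against.** The case against has several parts, and much of it stands.

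- **A reader might infer that the planned tables hide a marked CK value altogether.** They do not. If 59 patients sat at 1 × ULN and one at 20 × ULN (assumed), the mean would move by only 19/60 = 0.32 × ULN. But the maximum would read 20 and the SD would rise from 0 to 19/√60 ≈ 2.5 × ULN. Both are planned by visit and arm.
- **CK is not the only named monitor.** AST is named with it and is fully graded. That stands, although AST is tabulated as a liver test and does not indicate by itself which tissue it came from.
- **A reader might also infer that a muscle-derived AST rise would be taken for a liver signal.** The documents do not support this at case level. Protocol 7.6.1.8 asks for serum creatine phosphokinase (CK) in the work-up of raised aminotransferases. The Hy's Law definition also requires raised bilirubin and no other identified cause. Adverse events of special interest are assessed case by case (Protocol 7.6.2.3). What remains is that no planned table shows AST and CK together.
- **Adverse event tables may capture the case.** Only in part. Protocol 7.6.2.1 gives abnormal results as examples of adverse events when they are symptomatic, change treatment, or need added therapy or further work-up. A marked rise without symptoms may meet none of these.
- **The clinically important values summary still stands and covers more than CK.** Both are true. That gap is wider than CK, and CK matters here because the protocol singles it out. Without criteria or a table, the commitment does not yet produce a CK count.
- **Counts will be sparse.** This stands. With 0 of 60 patients, the exact one-sided 97.5% upper limit is 1 − 0.025^(1/60) = 6.0%, so intervals will be wide.

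**Conclusion.** The concern holds in a limited form. The number and percentage of patients with marked CK elevation per arm is not a pre-specified output, while the same count is planned for AST, the other enzyme named for the same purpose. The two provisions that could supply it, in Protocol 8.3.4 and SAP 3.5, are not made operational for CK, and SAP Table 4 records no change.

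The size is modest. No efficacy endpoint or test is affected. The counts can be derived from the listing, and the maximum would show that a marked value occurred. Protocol 1.2.2.2 describes the animal muscle findings as generally minimal, seen only at higher doses, unaccompanied by AST or CK rises, and absent after 3 months of dosing. Muscle injury is neither a named safety objective nor an event of special interest in this trial.

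The reading of the tables rests on the text of both documents. The numerical illustration rests on assumed CK values and assumed event rates.

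**What to change.** Add CK rows to the SAP 5.5.2 threshold table, based on each patient's worst post-baseline value, with the number and percentage of patients, the risk difference against placebo and its 95% confidence interval by arm. The sponsor should set the reporting cut-offs before unblinding. One option is to use the same multiples already listed for AST and ALT (above 3, 5 and 10 times ULN). These would be reporting categories only and would change no clinical rule.

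State in the SAP whether these rows implement, for CK, the clinically important values summary of Protocol 8.3.4 and the severity classification of SAP 3.5. If either is not to be produced, say so in Table 4.

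Optionally, show concurrent CK status for patients with AST above 3 times ULN, as a short table or listing.

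The cost is a few rows programmed from data already collected. Counts will probably be small and intervals wide, so the rows should be read as description.

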- P Hematology, blood chemistry, and urinalysis will be performed at all visits with a laboratory determination. Serologic tests for HIV, hepatitis B core antibody, hepatitis B surface antigen, and hepatitis C virus antibody, and a thyroid panel (TSH, FT3, and FT4) will be completed only at Screening. Laboratory tests can be repeated for up to 3 occurrences after Visit 2 to see if values return to normal range, but any abnormality must be resolved by the Baseline Visit.
- q To be conducted on Day -1 only if (1) the screening period exceeds 21 days; (2) a longer than 21-day prior medication washout is required, eg, fluoxetine > 20 mg/day; (3) per investigator's judgement. For women of pre-menopause, an inquiry of menses status should be made in the presence of macroscopic blood detection before submitting the sample to the central labs for microscopic examination.
- r Serum pregnancy testing will be performed in females of childbearing potential at Screening 1 and Day 42 (Visit 7). Urine pregnancy testing will be performed at Baseline (Day -1, dip stick).
- s Blood samples for PK will be collected on Day 28 (Visit 6) and on Day 42 (Visit 7) prior to dose administration, or at the time of early withdrawal, if within 3 days of last dose. Time of last dose and time of blood collection will be recorded. When possible, and if medically appropriate, blood samples should be collected for PK from patients who experience an SAE or overdose.

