# 2.2.3. Safety Endpoints

- Adverse events as characterized by type, frequency, severity, timing, seriousness, and relationship to study therapy
- Laboratory abnormalities as characterized by type, frequency, severity, and timing
- Vital signs including supine (after at least 5 min rest) and standing (after standing 1 min and 3 min), blood pressure and heart rate, weight, electrocardiogram (ECG), clinical laboratory evaluation, Discontinuation-Emergent Signs and Symptoms scale (DESS) scale, and Columbia Suicide Severity Rating Scale (C-SSRS) data

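### The laboratory shift table promises a low direction, but the only post-baseline value the SAP specifies is the maximum, so falls below range would be badly under-counted

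*SAP*

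**What the plan says.** SAP 5.5.2 (Clinical Laboratory Evaluation) builds the shift table in three consecutive sentences.

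- Categories: "Baseline and post-baseline blood chemistry and hematology tests will be classified according to normal ranges as low, normal, and high".
- Post-baseline value: "Shift of these tests from baseline to the maximum post-baseline values will be presented by treatment group".
- Direction: "If applicable, some laboratory tests have two directions: hypo and hyper, where both directions will be presented in the shift table".

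No sentence in the SAP defines a minimum, a nadir or a worst-in-direction value for this table, and the two-direction tests are not named.

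The same section also plans by-visit descriptive statistics (including the minimum) for actual value, change and percentage change. It sets threshold counts for four liver tests, and "All laboratory values will be presented in data listings". Protocol 2.2.3 makes this a stated safety endpoint: "Laboratory abnormalities as characterized by type, frequency, severity, and timing".

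**The concern.** A maximum is the right summary when the question is whether a value rose above range. It is the wrong one when the question is whether a value fell below range, because it takes the patient's highest value. The SAP promises a low direction and then names a value that works against it.

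At stake is the low side of the shift table for analytes where a fall matters, such as haemoglobin, neutrophils, platelets or sodium, all of which are in SAP Table 3. A nearly empty low category in every arm could be read as absence of a signal when it follows from the choice of summary value. Two programmers working from the same text could also produce materially different tables.

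**Working it through.** The plan gives no figure on this point, so there is nothing to reproduce. The check sets the text against the visit schedule, with one illustration that rests on assumptions.

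**1. Which values count as post-baseline.** SAP 3.2 defines baseline as the last value before first dose. SAP 5.5.2 does not limit post-baseline to time on drug. The laboratory row of Protocol Table 1 marks Day 14, Day 28, Day 42 and the visit 14 days after the last dose, and footnote p says "Hematology, blood chemistry, and urinalysis will be performed at all visits with a laboratory determination". A completer therefore has four scheduled post-baseline values, three on treatment and one off drug.

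**2. The rule as written.** The maximum of a set lies below the lower limit of normal only if every member does. So:

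| Day 14 | Day 28 | Day 42 | +14 days | Category of maximum | Category of minimum |
|---|---|---|---|---|---|
| low | low | low | low | low | low |
| low | low | low | normal | normal | low |
| normal | low | normal | normal | normal | low |
| high | low | normal | normal | high | low |

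Only the first row is counted as low by the maximum. The result needs no assumption about rates.

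**3. Does the direction sentence change this?** It says that both directions will be presented, where applicable, for some tests. It does not say which value feeds the hypo direction. A low/normal/high table of the maximum already has a low column, so both sentences can be met literally while most falls go uncounted.

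**4. Is the literal reading plausible?** SAP 5.5.3 applies the same construction to blood pressure: it tabulates the post-baseline maximum systolic value with a category below 90, and the maximum diastolic value with a category below 60. Pairing a maximum with a low category is thus a pattern in this SAP.

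**5. Illustration (assumed inputs, none from the documents).** Let p be the chance of a low value at each of four draws. If draws are independent:

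- low by the minimum (any draw low) = 1 − (1 − p)^4
- low by the maximum (all draws low) = p^4

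At p = 0.10 these are 1 − 0.9^4 = 0.344 and 0.1^4 = 0.0001. Repeated values on one patient are correlated, so the same quantities were simulated with equicorrelated normal draws (500,000 patients).

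| p per draw | Correlation | Low by minimum | Low by maximum |
|---|---|---|---|
| 0.05 | 0 (exact) | 18.5% | <0.01% |
| 0.05 | 0.8 | 10.6% | 1.3% |
| 0.10 | 0 (exact) | 34.4% | 0.01% |
| 0.10 | 0.5 | 25.8% | 0.9% |
| 0.10 | 0.8 | 19.3% | 3.2% |
| 0.20 | 0 (exact) | 59.0% | 0.16% |
| 0.20 | 0.8 | 34.3% | 8.4% |

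Correlation narrows the gap but does not close it in this range. Patients with fewer draws would show a smaller gap.

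**The case against.** The strongest reply is that the direction sentence would be pointless if the maximum also fed the hypo panel, so the natural joint reading is the worst value in each direction. That is good evidence of intent to display falls, and the sponsor may well programme it that way. It is still not a rule: the only value named is the maximum, and the sentence is qualified and names no test.

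A reader might infer that every test is judged by its maximum and that falls vanish from the report. The documents do not support that. Besides the direction sentence, low values can appear in the by-visit minima and the listings. Protocol 8.3.4 promises a summary of potentially clinically important laboratory values; SAP 3.4 mentions a summary of worst change from baseline; SAP 3.5 grades laboratory values as mild, moderate or severe; and laboratory abnormalities with clinical consequences can be recorded as adverse events (Protocol 7.6.2.1) and counted as such.

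For the same reason it would be wrong to call the shift table the only planned patient-level count of non-liver abnormalities. What stands is narrower. None of these is an SAP-specified count, by arm, of patients whose non-liver values fell below range. The by-visit minimum is one extreme value per arm and visit, and listings make no comparison. The SAP gives neither criteria nor a table for potentially clinically important laboratory values, and its Section 6 does not record dropping them. It does not define worst change or specify such a laboratory table in 5.5.2.

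It is also fair to say that the target organs in Protocol 1.2.2.2 are skeletal muscle and liver, monitored through enzymes that rise, and that the documents describe no haematological or sodium signal. That limits the likely consequence but does not make the rule correct.

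**Conclusion.** The concern holds in this form: the SAP promises a low direction and specifies a summary value that defeats it. It is wrong as written, because a value is stated and works against the stated aim; this goes beyond missing detail. Followed literally, a shift to low requires every post-baseline value to be low, including the off-drug draw 14 days after the last dose.

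That conclusion rests only on the wording of SAP 5.5.2 and the schedule in Protocol Table 1. The size of the under-count cannot be taken from the documents; the percentages above depend on assumed rates and correlations and describe a maximum-only table. No efficacy result, sample size or error rate is affected. The point should be corrected before the shift tables are programmed.

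**What to change.** Replace the sentence on the maximum in SAP 5.5.2 with: 'Shifts will be presented from baseline to the minimum post-baseline value for the low (hypo) direction and to the maximum post-baseline value for the high (hyper) direction.' Name the tests to be shown in both directions, for example haemoglobin, neutrophils, platelets, sodium, potassium and glucose.

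The cost is one SAP sentence, a short list of tests and one further shift-table panel for each two-direction test. No new data are needed. Showing on-treatment values separately from the 14-day follow-up value is an optional display choice, not part of the correction.
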